6.10. Agent Destruction/Disposal

Unused drug should be destroyed on site following site institutional policies and procedures.

7. CLINICAL EVALUATIONS AND PROCEDURES

7.1 Schedule of Events

At each participating Research Base site, medical charts will be screened to determine potential eligibility by physicians (including residents or fellows, if applicable), research nurses, or clinical research associates. This information should be recorded on the Screening Form. Patients identified as potentially eligible will then be asked to consider joining the study. Patients meeting initial eligibility criteria and who agree to participate in the study will sign informed consent and then undergo a baseline nurse exam, laboratory tests and quality of life tests. At baseline, 6, and 24 months (or within 27 months), the entire battery of neurocognitive tests and questionnaires will be administered by a trained and certified examiner. At 12 and 18 months participants will be contacted by phone to assess toxicities and medication compliance. Quality of Life Questionnaires will be completed via mail. Patients will be instructed in the self-administration of the study agent. Patients will take one pill daily beginning within 48 hours (2 days) prior to the start of chemotherapy. It may be helpful if the patient receives 2 doses prior to first chemotherapy treatment and those 2 doses be at least 12 hours apart. If necessary however due to time constraints, the patient may be given 2 tablets at the same time at least 90 minutes prior to first chemotherapy treatment. Potential side effects and risks are described in Section 6.2. Adverse event reporting is described in Section 10. Study outcomes will be assessed at baseline, after 6 months and at the end of 24 month (or within 27 months). Patients completing at least 24 months of study medication but no more than 27 months will be followed for an additional 30 days after the last dose of study medication to evaluate any study related adverse events.

7.2. Screening/ Baseline Evaluations

Due to the scheduling complexity of protocol requirements prior to the start of the first chemotherapy treatment, screening and baseline procedures and randomization may be performed at the sites discretion once the patient has signed the consent. The patient should be registered within 30 days of screening labs.

Subjects will be checked for height, weight, waist circumference, heart rate and blood pressure. Body Mass Index (BMI) will be calculated at the data center. Patient physical exam including peripheral edema, smoking status and family history will be collected by study personnel.

Waist circumference Measuring Directions

- Patient should be instructed to not hold their breath.
- The measuring tape should be secure but not tight.
- The area being measured can be found by placing the hands on the waist and moving them downward until the top curve of the hip bone can be felt.
- The area being measured can be found by placing the hands on the waist and moving them downward until the top curve of the hip bone can be felt.
- Place the tape measure around the top of the hip curve and wrap around at the level of the belly button. (This may not be the same level as the top of the pants.)
- Record this measurement in inches on the flow sheet.

Study personnel will download the CV Risk Calculator according to specifications in Appendix 3. After collecting the appropriate information, it will be entered in the CV Risk Calculator. Note: If the patient is < 40 years old, data cannot be entered in CV Risk Calculator. The result will be documented on the flow sheet and the Physician Statin Update Letter to be mailed to the treating and primary care physician. **If the study participant should have statin therapy initiated, the study coordinator should complete the Open Label Form (Appendix 12) and submit to the Data Management Center.**

Serum and blood derived biomarkers - A blood sample of approximately 4 tablespoons will be taken from a vein in the arm/central line for lab analysis.

Statins exert pleiotropic effects (modulation of systemic inflammation and the neurohormonal axis) that in other models of heart failure influence LV function,^{57,58} and have been modulated in pilot animal studies.¹⁴ In this study, we will determine the relationship between Anthracycline-based therapy administration, statin use and biomarker evidence of systemic inflammation⁵⁹ and neurohormonal axis activation.⁶⁰ We will associate these relationships with changes in both LV and vascular function.

Labs for future testing - Participants who consent to have blood stored for future research will have an additional 1 tablespoon of blood drawn. These labs will be picked up and processed by LabCorp. Blood samples will be shipped and stored with a unique identifier and will not include any information protected by HIPAA regulations. LabCorp's Bio-repository for blood samples is located in Kannapolis, North Carolina.

MRI Variables - MRI exams will be accomplished according to previously published techniques described on the Research Base website under "Helpful Guides" located in the Appendices section. Our research group and [name] (PI) has extensive experience developing and utilizing these techniques in single center or multi-center efforts including the Jackson Heart Study ([name] is Co-PI for the core lab) and the MESA study.

LVEF is the primary outcome because it is the most widely clinically implemented assessment of LV performance, and is used to guide therapeutic intervention. LVEF has limitations as it can vary dependent on LV pre-load or after-load. To account for these limitations we are utilizing MRI to measure LVEDV (pre-load) and PWV (after-load). Also, we will perform advanced assessments of LV contractility including myocardial strain which is utilized in other NHLBI studies (such as MESA). This will allow us to measure systolic performance independent of LV pre-load and enable cross. Aortic distensibility will be assessed as an exploratory aim.

The MRI is for study purposes only, the imaging results will not be reviewed at the site. The WF NCORP Research Base will send a clinical update when the MRI is reviewed and/or alert the site study staff if an unrecognized myocardial infarction was identified.

At baseline, if a routine standard of care ECHO or MUGA is obtained and available at the time of enrollment, the LVEF result should be documented on the enrollment form. If the LVEF result is available after enrollment, record the result on the flow sheet. .

An MRI should be obtained between 5 and 7 ½ months. All anthracycline therapy should be completed and tissue expanders (if applicable) removed before obtaining the cardiac MRI. For time periods outside of these ranges, special permission for extenuating circumstances (e.g., significant healthcare issue warranting hospitalization) may be obtained by direct contact with [name], the study PI. If it is determined a patient cannot have a 6 month (5-7 ½ month) MRI, the patient will continue on study as per protocol.

The 24 – 27 month MRI should be obtained within 30 days prior to the last dose of study medication. For time periods outside of these ranges, special permission for extenuating circumstances (e.g., significant healthcare issue warranting hospitalization) may be obtained by direct contact with [name], the study PI.

Due to unknown risks and potential harm to the unborn fetus and because some methods of birth control are not 100% reliable, it is suggested that women of childbearing potential take a pregnancy test prior to each MRI exam, as written in the informed consent form. It is also suggested that a

negative serum or urine pregnancy test be performed within 10 days of each MRI exam. Each site should follow their institution's policies.

MRI may be performed without contrast but it is preferred contrast be used to better define the cardiac structures. If the site has a signed contract with Bracco and ProHance is supplied, the site will be responsible for maintaining a careful record of the inventory and disposition of the ProHance® received.

Neurocognitive Function

Cognition and Quality of Life

Once eligibility has been established the neurocognitive test battery and the study questionnaires will be completed. Individual components of the full battery are described below. Tests have been selected to represent a range of cognitive abilities which have been reported in the literature to be affected by chemotherapy including attention, verbal memory, working memory, executive functions, speed of mental processing and verbal fluency. An abbreviated battery consisting of two tests has been developed for the baseline assessment to reduce participant burden (see below). All cognitive testing will be performed by a trained and certified research assistant blinded to treatment assignment. The WF NCORP Research Base has conducted training workshops and produced videos for administering this cognitive test battery for our completed trials among irradiated brain tumor patients and breast cancer patients exposed to chemotherapy, and maintains a stringent certification process (Section 8.2).

An abbreviated battery of the cognitive tests and shorter versions of quality of life questionnaires will be used at baseline to reduce participant burden and due to time constraints related to the start of the first chemotherapy treatment. The shorter battery includes the same tests in the longer version used at 6 and between 24 - 27 months to ensure we have adequate consistency across assessment points. Each cognitive test has adequate psychometric properties and has been used in cancer research including large national and international clinical trials (Ahles & Saykin, 2002; Mehta et al., 2002; Meyers et al., 2004). The entire cognitive test battery takes 10 minutes to administer at baseline and 30 minutes to administer at 6 months and 24 months. It will be administered with the questionnaires which takes 10 minutes at baseline 6 months and 24 months.

Controlled Oral Word Association Test (COWA)

The COWA (Benton & Hamsher, 1976) measures speed of mental processing, verbal fluency, and executive function. Subjects are asked to name as many words as possible all beginning with a specified letter. A total of three trials are administered, each with a different letter (C-F-L). The score on the COWA is the total number of words named across the three trials minus repetitions. The COWA has two equivalent forms (C-F-L and P-R-W) that will reduce practice effects. Internal consistency reliability ($\alpha=0.83$) and test-retest reliability ($r = 0.74$) are excellent (Ruff et al., 1996).

Hopkins Verbal Learning Test-Revised (HVLTR)

The HVLTR measures verbal learning and memory. It consists of a 12-item word list which is read to subjects on three successive learning trials. Free recall scores are recorded for each learning trial. After a 20-minute interval during which subjects complete other non-interfering tasks and questionnaires they are asked to recall the target words. Lastly, a yes/no recognition task is then presented in which subjects are asked to identify all target words by responding "yes," and to reject 12 non-target words by responding "no." The HVLTR has six equivalent alternate forms (Brandt, 1991) to minimize confounding by practice effects. Test-retest reliability of the HVLTR is quite good (0.74). The test is brief, taking only 10 minutes to administer, and it is well-tolerated by compromised (geriatric and dementia) populations. Scores for immediate recall (total of three trials), delayed recall (total number of words recalled after 20 minutes), and recognition (total number of words correctly identified) will be the variables derived from the HVLTR.

Trail Making Test, Parts A & B (TMT-A, TMT-B)

Part A of the TMT(Reitan, 1958) measures attention and visual motor skills and processing speed and requires subjects to connect 25 numbered circles in the proper sequence (1-2-3-...) as quickly as possible. TMT-B is similar except subjects are required to connect dots in an alternating numerical and alphabetical sequence (1-A-2-B-...). TMT-B with its added complexity and set shifting requirements is a widely used measure of executive function. The score for TMT-A and TMT-B is the total time in seconds required to complete the task. Scores can also be generated for number of errors and number of circles correctly connected. The TMT has excellent reliability and validity (Reitan, 1992).

Digit Span Test (DST)

The DST (Wechsler, 1981) assesses attention and working memory. It requires respondents to repeat back gradually increasing spans of numbers. Seven series of two spans of each length are presented and repeated backwards. A total score is the sum of the longest span backwards.

Self-Report Questionnaires:

The Patient Reported Outcomes Measurement Information System (PROMIS) is a collection of well-validated, brief, fee-free instruments assessing key patient reported outcomes related to this study. Each PROMIS scale has excellent psychometric properties (reliability and validity) and are being used in many clinical trials and observational studies. For this study, we will include the short forms for:

PROMIS Applied Cognition – General Concerns – Short Form 4a (4 items)

PROMIS Applied Cognition – Abilities – Short Form 4a (4 items)

PROMIS Fatigue – Short Form 4a (4 items)

PROMIS Mood – Emotional Distress - Anger – Short Form 5a (5 items)
Emotional Distress - Anxiety – Short Form 4a (4 items)
Emotional Distress - Depression – Short Form 4a (4 items)

PROMIS Pain Intensity - Short Form 3a (3 items)

PROMIS Pain Interference - Short Form 4a (4 items)

PROMIS Sleep Disturbance - Short Form 4a (4 items)

PROMIS Physical Function - Short Form 4a (4 items)

PROMIS Ability to Participate in Social Roles and Activities - Short Form 4a (4 items)

The total administration time for these questionnaires is 10 minutes.

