****** Due to the scheduling complexity of protocol requirements prior to the start of the first chemotherapy treatment, baseline procedures and randomization may be performed at the sites discretion once the patient has signed the consent. The patient should be registered within 30 days of screening labs.

Study Sample: n=278

Study Duration: at least 24 months per subject but no greater than 27 months.

Patients completing at least 24 months of study medication will be followed for an additional 30 days after the last dose of study medication to evaluate any study related adverse events.

Brief Eligibility Criteria:

- Stage I-III breast cancer (including inflammatory and newly diagnosed recurrent breast cancer) or lymphoma Stage I-IV
- Scheduled to receive chemotherapy with any anthracycline
- Age: ≥ 21 years of age

INDEX

COVER PAGE

SCHEMA

1. OBJECTIVES	9
2. BACKGROUND.....	11
3. SUMMARY OF STUDY PLAN.....	15
4. PARTICIPANT SELECTION	17
5. AGENT ADMINISTRATION	19
6. PHARMACEUTICAL INFORMATION.....	21
7. CLINICAL EVALUATIONS AND PROCEDURES	31
8. PROTOCOL SPECIFIC TRAINING REQUIREMENTS.....	38
9. SPECIMEN MANAGEMENT	39
10. REPORTING ADVERSE EVENTS.....	39
11. STUDY MONITORING	42
12. STATISTICAL CONSIDERATIONS	44

REFERENCES

Consent Form
FDA Letter

APPENDICES

- | | |
|--|---|
| 1. Data Submission Checklist | 12. Physician Statin Update
(Includes Open Label Form) |
| 2. Eligibility Checklist-Enrollment | 13. Baseline Neurocognitive Booklet |
| 3. CV Risk Calculator and Instructions | 14. 6 Month Neurocognitive Booklet |
| 4. Patient Medication Diary | 15. 12 Month Booklet |
| 5. Screening Form | 16. 18 Month Booklet |
| 6. Flow Sheet / Addenda | 17. 24 Month Neurocognitive Booklet |
| 7. Current Medication Form | 18. Early Withdrawal Form |
| 8. Radiation Treatment Form | 19. 1 Month Contact Form |
| 9. Chemotherapy Treatment Form | |
| 10. Lab Instructions | |
| 11. Telephone Contact Form | |

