12.5. Secondary Analyses: Once the primary efficacy analysis is completed, secondary efficacy variables will be examined to provide insight into mechanisms by which statins may influence LVEF. These include: LVESV and strain (reflective of LV contractility), LVEDV (reflective of LV pre-load), PWV and aortic wall thickness (reflective of LV after-load), and LVECV (a measure of myocellular replacement fibrosis). In addition, we will measure a series of subclinical biomarkers, including serum lipids (LDL, TC, HDL), glucose, serum troponin I, CRP, IL-6, TNF- α , renin, and aldosterone at the 6- and 24-27 month endpoints. For each, we will fit ANCOVA models that will examine the 24-27 month endpoints adjusted for baseline assessments, followed by ANCOVA models that also include patient-level characteristics. Next, we will fit repeated measures ANCOVA models that incorporate intermediate (6-month) time point assessments. This approach will be repeated for the cognitive and patient reported outcomes. The latter analyses will also include data for the 12 and 18 months follow-ups.

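### Section 12.5 does not name the randomisation strata in the secondary models and, if the shortened baseline battery in 7.2 is what is given, has no model for cognitive tests without a baseline

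*Combined protocol and SAP*

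**What the plan says.** All references are to the combined protocol and SAP.

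**Models.** Section 12.1 stratifies randomisation by cancer type and planned anthracycline dose. Section 12.3 includes the stratification factors, with dose as planned, in the primary ANCOVA of LVEF. The additional LVEF models later in 12.3 adjust for baseline LVEF and patient characteristics; the examples given are age, cancer type, stage and race. Section 12.5 specifies, for secondary outcomes, "ANCOVA models that will examine the 24-27 month endpoints adjusted for baseline assessments, followed by ANCOVA models that also include patient-level characteristics", then repeated measures models. It extends this to the cognitive and patient reported outcomes and excepts none.

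**Baseline testing.** Section 7.1 says that at baseline, 6 and 24 months "the entire battery of neurocognitive tests and questionnaires will be administered by a trained and certified examiner". Section 7.2 says: "An abbreviated battery consisting of two tests has been developed for the baseline assessment to reduce participant burden". It points to a description below, but the test descriptions that follow do not say which two tests are meant. It adds: "The shorter battery includes the same tests in the longer version used at 6 and between 24 - 27 months". It also says that "shorter versions of quality of life questionnaires will be used at baseline". Cognitive testing is timed at 10 minutes at baseline and 30 minutes later. For the questionnaires the text reads: "It will be administered with the questionnaires which takes 10 minutes at baseline 6 months and 24 months".

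**Test lists.** The first secondary objective in Section 1 names six instruments. Section 7.2 describes four: COWA, HVLT-R, Trail Making and Digit Span. The Rey-Osterreith Figure and Grooved Pegboard are not described there.

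**The concern.** There are two separate gaps in the secondary analysis.

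First, stratified randomisation removes between-stratum variation from the treatment comparison. A model that leaves the strata out still counts that variation as residual error. If the strata are prognostic, the reported standard error is too large and some power is lost. The plan avoids this for the primary LVEF model and gives no reason for treating the secondary outcomes differently.

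Second, a baseline-adjusted model needs a baseline. If only two cognitive tests are given before chemotherapy, the remaining tests have none, by design. Section 12.4 deals with drop-outs, not with baselines that were never scheduled. The repeated measures step does not help, because the version described in 12.3 also carries baseline as a fixed effect. The analyst would then choose covariates for part of a stated secondary objective with the data in hand.

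**Working it through.** **1. Reproduce the plan's figure.** Section 12.6 gives the detectable difference as σ × √(2(1 − r²)/n) × (z for two-sided α = 0.05 + z for power). The inputs are σ = 7.7, r = 0.5, n = 100 per group and 80% power.

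- Sum of z values: 1.960 + 0.842 = 2.8016.
- In SD units: √(2 × 0.75/100) × 2.8016 = 0.343.
- For LVEF: 7.7 × 0.343 = 2.64, as in Table 5.

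The plan gives no power figure for cognitive or patient reported outcomes, so the rest is in SD units.

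**2. Leaving out the strata.** Let s be the share of the variance remaining after baseline that the strata explain. The documents give no value, so 2%, 5% and 10% are assumptions, as is r = 0.5 for these outcomes. The standard error is too large by 1/√(1 − s). With strata included, the detectable difference is √(2 × 0.75 × (1 − s)/100) × 2.8016.

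| s (assumed) | SE factor | Detectable difference with strata (0.343 without) |
|---|---|---|
| 0.02 | 1.010 | 0.340 SD |
| 0.05 | 1.026 | 0.334 SD |
| 0.10 | 1.054 | 0.326 SD |

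The plan has some evidence on dose. Section 2.4 reports pilot correlations of 0.01 to 0.05 between doxorubicin-equivalent dose and change in LV or aortic measures. At the upper end r² = 0.05² = 0.0025, and 1/√0.9975 = 1.001. For dose on cardiac outcomes the factor is therefore about 1.00. Those data concern dose received and say nothing about cognition or cancer type.

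**3. Check by simulation.** In each trial 278 patients were randomised in permuted blocks within strata and 78 were lost at random, with r = 0.5 and a true effect of 0.343 SD (5,000 trials per setting). Block size 4, 85% breast cancer and an even dose split are assumptions. Four strata follow 12.1 (cancer type by dose); six follow the schema, which also separates doxorubicin from epirubicin in breast cancer.

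| s | Power, 4 strata: without → with | Power, 6 strata: without → with |
|---|---|---|
| 0 | 0.801 → 0.798 | 0.797 → 0.795 |
| 0.05 | 0.790 → 0.803 | 0.802 → 0.816 |
| 0.10 | 0.786 → 0.823 | 0.802 → 0.833 |

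The gain is 1.3 to 1.4 points at 5% and 3.1 to 3.7 points at 10%. The cost is 0.2 to 0.3 points if the strata explain nothing. At s = 0.10, type I error moves from 0.042 to 0.051 (four strata) and from 0.039 to 0.045 (six). Without strata the test is slightly conservative, not anti-conservative.

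**4. Which tests have a baseline?** Section 7.2 is the more specific text and its times support it: 10 minutes at baseline against 30 later, while HVLT-R alone is put at 10 minutes. The sentence about the shorter battery containing the same tests as the longer one is most naturally read as saying that the two baseline tests recur later. It gives the other tests no baseline. On that reading 4 − 2 = 2 of the tests described in 7.2 have none.

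The questionnaires are different. They are called shorter at baseline but take 10 minutes at every visit. The full set of 11 PROMIS forms (4+4+4+5+4+4+3+4+4+4+4 = 44 items) is timed the same: "The total administration time for these questionnaires is 10 minutes". No scale can be identified as missing at baseline.

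**5. What a specified fallback could recover.** With no covariates the detectable difference is √(2/100) × 2.8016 = 0.396 SD. If the strata, age and collected baseline scores explain an assumed 10%, 20% or 30% of variance, it is 0.376, 0.354 or 0.331 SD.

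**The case against.** The strongest reply has four parts.

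- **12.5 speaks of baseline assessments, not of each outcome's own baseline.** Read loosely, it already permits adjustment for whatever baseline scores exist. This is fair as to wording. Own-baseline adjustment is the natural reading, since the approach is modelled on LVEF adjusted for LVEF. Even on the loose reading the covariates are not specified.
- **Step two already allows age and cancer type.** This stands. A reader might infer that 12.5 shuts out the strata entirely; the text does not support that. What is missing is both factors at the first step and planned dose at either step. The additional LVEF models in 12.3 share the gap on dose, so 12.5 follows the plan's pattern for non-primary models.
- **The strata benefit is assumed.** This also stands. The 2% to 10% range has no source in the documents, and the pilot data suggest almost no gain from dose on cardiac measures. The case for adding strata is consistency with the design at almost no cost, not a demonstrated power problem.
- **The baseline gap depends on 7.2 governing.** Agreed. The "Baseline Neurocognitive Booklet" (Appendix 13) is not among the documents available here and may name the two tests. It might settle which tests have a baseline, but naming tests would not supply a model for those without one.

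**Conclusion.** The point holds as an inexpensive improvement to the secondary analyses.

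The strata omission is plain in the text. Its effect is small: a standard error 1.01 to 1.05 times too large under the assumed shares, and about 1.00 for dose on cardiac measures. The missing-baseline problem is conditional. If 7.2 governs, the stated ANCOVA cannot be fitted for 2 of the 4 tests described there; if 7.1 governs, the problem disappears. The contradiction between 7.1 and 7.2, and the mismatch in the test lists, exist either way.

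Three stronger readings should be resisted. The cognitive comparison is not biased: post-baseline scores compared between randomised groups remain valid without a baseline covariate. The primary LVEF analysis is not affected, because 12.3 names both its baseline and the strata. Nor do the documents show that any patient reported scale lacks a baseline, since the stated times point the other way and a shorter form could still give a score. What is at stake is modest precision and prespecification.

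**What to change.** 1. **Strata.** In 12.5, add cancer type and planned dose stratum, coded as used in the randomisation, to every model at every step. Do the same for the additional LVEF models in 12.3. The coding needs stating, because 12.1 and the schema suggest different numbers of strata.
2. **Cognitive tests.** Keep own-baseline ANCOVA wherever a baseline exists. For any test without one, prespecify ANCOVA of the 24-27 month score, and the matching repeated measures model, on treatment, strata, age and the two baseline cognitive scores collected.
3. **Patient reported outcomes.** If any scale proves to have no baseline, use the same models with treatment, strata, age and all patient reported scores collected at baseline.
4. **Text.** Reconcile 7.1 with 7.2, name the tests and scales given at baseline, and align the instrument list in the first secondary objective (Rey-Osterreith Figure, Grooved Pegboard) with the battery actually used.

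The cost is protocol and SAP wording only, with no added tests, visits or patients. Strata and age are already recorded, and the other covariates are limited to scores that are collected. If 7.1 governs, the fallback models in items 2 and 3 are not needed; items 1 and 4 still apply. Precision lost by not testing at baseline is a design choice that this change does not reverse.
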